#### **5.12. Data analysis:**

Statistical analysis will be performed using Statistical Package for Social Science (SPSS) version 27.0 (IBM Corp., Armonk, NY, USA). Baseline continuous variables such as age, monthly income, height, weight, BMI, blood pressure, duration of hemodialysis, and biochemical markers (serum calcium, phosphate, parathyroid hormone, and serum creatinine) will be expressed as mean  $\pm$  standard deviation (SD) or median with interquartile range (IQR) depending on data distribution, while categorical variables such as sex, presence of diabetes mellitus (DM), hypertension (HTN) use will be presented as frequencies and percentages. Normality of continuous variables will be assessed using the Shapiro-Wilk test. For comparison between the control and experimental groups, independent samples t-test or Mann-Whitney U test will be applied for continuous variables, depending on their distribution, and Chi-square test or Fisher's exact test will be used for categorical variables. Biochemical parameters (serum calcium, phosphate, PTH, and serum creatinine) at baseline and after 12 weeks of follow-up will be compared within each group using paired t-test or Wilcoxon signed-rank test as appropriate. A p-value of less than 0.05 will be considered statistically significant.

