### **Specific objectives:**

1. To detect and compare the reduction of serum parathyroid hormone (PTH) levels following treatment with intravenous doxercalciferol and oral calcitriol in hemodialysis patients.
2. To assess the changes in serum calcium and phosphate levels associated with each treatment modality.
3. To evaluate the incidence of treatment-related hypercalcemia and hyperphosphatemia in both treatment groups.
4. To compare the adverse events and efficacy profiles of intravenous doxercalciferol and oral calcitriol in the management of secondary hyperparathyroidism in hemodialysis patients.

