### 5.8. Sample size:

To calculate sample size for case control, study the comparison between two means, the following formula was followed (Hoque, 2014)

$$n = \frac{(Z_a + Z_b)^2 \cdot (s_1^2 + s_2^2)}{(m_1 - m_2)^2}$$

Here,

$m_1$  = 342.0 (mean of iPTH in oral cholicalciferol group)

$m_2$  = 279.0 (mean of iPTH in intravenous doxercalciferol group)

$s_1$  = 42.0 (Standard deviation of oral cholicalciferol group)

$s_2$  = 90.0 (Standard deviation of intravenous doxercalciferol group)

$Z_a$  = Z value (two tail) of standard normal distribution at 95% confidence level or 5% level of significance = 1.96 (when  $\alpha = 0.05$  at 5% level of significance)

$Z_b$  = Z value at 90% power = 1.28 (when  $\beta = 0.1$  and Power =  $1 - \beta$ )

Therefore,

$$\begin{aligned} n &= \frac{(1.96 + 0.85)^2 \cdot \{(42.0)^2 + (90.0)^2\}}{(342.0 - 279.0)^2} \\ &= 42.8 \end{aligned}$$

This study is a follow-up study, necessitating a 15% increase in the sample size to compensate for dropout cases during the follow-up period. Consequently, the total sample size amounted to 49 cases, comprising 43 estimated sample size plus an additional 6.

Therefore, total sample size was 98 ( $49 \times 2$ ).

All values were taken from Aggarwal et al. (2011).

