All laboratory analyses will be conducted in an ISO-certified laboratory, ensuring accuracy and standardization of results.

**Treatment:** The treatment phase will last for twelve weeks. Experimental subjects will receive an intravenous loading dose of doxercalciferol 4 micrograms after dialysis, in addition to their standard routine medications. Each Dose of doxercalciferol will be given after skin sensitivity test. Skin sensitivity test will be performed by a small amount of doxercalciferol inject intradermally → wait 10-15 minutes → see for localized swelling and redness. Though skin sensitivity test negative despite patients may developed anaphylactic reaction, Then following measure will be taken. Prevent further contact with allergen, ensure airway patency, anti histamine, hydrocortisone, nebulize with sulbutamol, adreline, i/v fluids. Patients in the control group will receive oral calcitriol 0.25 micrograms once daily, along with their standard routine medications.

**Evaluation of the patient at 6 Weeks:** The patients will be followed up at 6 weeks ( $\pm 2$  days) and will instructed to report immediately in case of any advance events following consumption of the drug. Tolerability will be assessed using an adverse event profile (adverse events, serious adverse events). Safety population consist of subjects who receive at least one dose of study medication. Body weight and sitting blood pressure will be evaluated. patients will be removed if any of the withdrawals mentioned above are observed, and appropriate management will be initiated in the nephrology department of CMCH.

**Follow –up and outcome assessment:** All the patients will be examined again after 12 weeks ( $\pm 2$  days) The same biochemical parameters—serum calcium, serum phosphate, iPTH,—will be reassessed under the same collection and analysis protocols. These follow-up results will be compared with baseline values to evaluate the relative efficacy of IV doxercalciferol versus oral calcitriol in controlling SHPT and maintaining mineral balance. All data, including demographic, clinical, and laboratory results, will be systematically documented in a Case Record Form (CRF) to ensure completeness and integrity of the dataset.

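### Section 5.12 plans no baseline-adjusted comparison of iPTH between arms, leaves the compared quantity unnamed, and its within-arm tests cannot show relative efficacy

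*Protocol*

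**What the plan says.** The first specific objective is a contrast between arms: "To detect and compare the reduction of serum parathyroid hormone (PTH) levels" after the two treatments. The research hypothesis in 3.2 is also between arms.

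Section 5.12 then gives two kinds of test.

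- Between arms: "independent samples t-test or Mann-Whitney U test will be applied for continuous variables, depending on their distribution". Normality is judged by the Shapiro-Wilk test. The sentence covers continuous variables in general and does not say whether the 12-week value or the change from baseline is analysed. No covariate is mentioned.
- Within arms: calcium, phosphate, PTH and creatinine "at baseline and after 12 weeks of follow-up will be compared within each group using paired t-test or Wilcoxon signed-rank test as appropriate".

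The threshold is the same throughout: "A p-value of less than 0.05 will be considered statistically significant".

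Under follow-up and outcome assessment, section 5.11 adds: "These follow-up results will be compared with baseline values to evaluate the relative efficacy of IV doxercalciferol versus oral calcitriol". The Part C summary repeats the independent t-test for means. Section 5.8 sizes the trial on a difference between two group means, with no baseline term. Baseline and 12-week iPTH, calcium and phosphate are all on the case record form.

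**The concern.** Sections 5.11 and 5.12 do not line up with the objective. The question is whether one drug lowers iPTH more than the other. The only analysis that 5.12 ties by name to the before-and-after values is done separately in each arm, and 5.11 says that comparison with baseline is how relative efficacy will be evaluated. An analyst who followed the two sections literally could report a significant fall in one arm and a non-significant fall in the other, and treat that as the comparison. It is not one, because neither p-value measures the difference between arms.

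The between-arm test that is planned leaves two things open. The first is the quantity compared: a test on the 12-week value and a test on the change have different precision. The second is the form of the test. The Shapiro-Wilk switch lets the data decide whether a difference in means or a shift in ranks is estimated. Neither version adjusts for baseline iPTH, usually one of the stronger predictors of the follow-up value and here available at no extra cost.

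**Working it through.** **The plan's own figure.** Section 5.8 gives α = 0.05 two-sided, means of 342 and 279 (difference 63), SDs of 42 and 90, "Z value at 90% power = 1.28", and a result of 42.8 per arm.

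- Formula as printed, with 0.85: (1.96 + 0.85)² × (42² + 90²) / 63² = 19.6.
- With the listed 1.28: (1.96 + 1.28)² × (42² + 90²) / 63² = 26.1.
- With 1.28 and SD 90 in both arms: (1.96 + 1.28)² × (90² + 90²) / 63² = 42.85.

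Only the third matches, so power is shown below under both readings of the SD. That mismatch is a separate problem and is not pursued here. Completers per arm are taken as 49 × 0.85 = 41.65, about 42.

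**Within-arm tests used as a comparison.** Suppose both arms have the same true fall, expressed in SDs of the within-patient change. Each paired t-test (n = 42, two-sided 5%) has power p, from the noncentral t distribution with noncentrality fall × √42. The chance that exactly one arm is significant is 2p(1 − p).

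| True standardised fall | p | Exactly one arm significant |
|---|---|---|
| 0.2 | 24% | 37% |
| 0.3 | 48% | 50% |
| 0.4 | 72% | 41% |
| 0.5 | 89% | 20% |
| 0.8 | 99.9% | 0.2% |

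The curve cannot exceed 50%, and it falls quickly once the common fall is large.

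**Baseline adjustment.** Let ρ be the correlation between baseline and 12-week iPTH within arms. The documents do not give it, so it is assumed here. Relative to a t-test on 12-week values, with equal SDs at the two times:

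- ANCOVA multiplies the residual variance by (1 − ρ²): 0.91, 0.75 and 0.51 at ρ = 0.3, 0.5 and 0.7.
- A t-test on change multiplies it by 2(1 − ρ): 1.4, 1.0 and 0.6.

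Power for a difference of 63 with 42 per arm (noncentral t), **assuming SD 90 in both arms**; the unadjusted noncentrality is 63 / (90 × √(2/42)) = 3.21:

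| ρ | 12-week value only | Change score | ANCOVA |
|---|---|---|---|
| 0.3 | 88.7% | 76% | 91% |
| 0.5 | 88.7% | 88.7% | 95.5% |
| 0.7 | 88.7% | 98.4% | 99.3% |

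**With the printed SDs**, the root-mean-square SD is √((42² + 90²)/2) = 70.2 and unadjusted power is already about 98%. ANCOVA at ρ = 0.5 gives 99.7%, a gain of about 1.5 points.

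So under the SD-90 reading the unnamed quantity alone moves power between 76% and 88.7% at ρ = 0.3. ANCOVA is above both alternatives at every ρ shown.

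**The case against.** The strongest reply is that a proper between-arm test is already in 5.12. Its sentence on continuous variables is not restricted to baseline, PTH is listed as a continuous variable in 5.9, and the hypothesis and first objective are both between arms. An unadjusted t-test or Mann-Whitney test in a 1:1 randomised trial is valid. This stands, and it sets the weight of the point.

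Several stronger readings are tempting but are not supported.

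- *A reader might infer that the plan ignores baseline iPTH.* The paired tests use it, and an objective framed as a reduction allows a between-arm test on change. What can be said is that no stated between-arm test adjusts for it.
- *A reader might infer that efficacy will be declared from the paired tests.* No sentence says so. The 5.11 wording also fits a between-arm comparison of changes. It is ambiguous and should not be left so.
- *A reader might infer that selecting patients on iPTH above 300 pg/mL biases the result.* Regression to the mean can inflate the fall seen within each arm, but in expectation it acts equally on both randomised arms and does not bias their comparison.
- *A reader might take 50% as the error rate.* It is the peak of the curve. The Introduction cites suppression of over 40% in 58% of calcitriol patients. If log changes are normal with an assumed SD of 0.5, that implies a mean log change of about −0.61, a standardised fall of about 1.2. Discordance there is practically nil.
- *A reader might infer that a log scale is required.* The planning figures imply coefficients of variation of 12% (42/342) and 32% (90/279), and the plan already provides for non-normal data. Log is a reasonable choice for iPTH, not a demonstrated necessity.

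It can also be said that model details belong in a statistical analysis plan. That holds for detail the protocol leaves out. Here 5.12 does name the tests, and the point concerns what it names.

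**Conclusion.** The point holds as a free improvement and not as a must-fix for bias. The stated between-arm test is valid but unadjusted, its form depends on a normality pre-test, and the quantity it compares is not named. The within-arm tests cannot establish that one drug is better than the other, yet the 5.11 sentence can be read as giving them that role.

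The size of the benefit is uncertain because ρ is not in the documents. If the SD is 90 in both arms, the gain in power over a test of 12-week values is about 3, 7 and 11 points at ρ = 0.3, 0.5 and 0.7. If the printed SDs of 42 and 90 are right, power is already about 98% and the gain is small. The risk from misread paired tests runs from 50% down to 0.2% over the range of common falls shown.

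**What to change.** In 5.12, name one primary between-arm analysis: week-12 iPTH by ANCOVA with treatment and baseline iPTH, two-sided 5%, reported as an estimate with a 95% confidence interval. Fix the scale in advance in place of the Shapiro-Wilk switch for this endpoint. If log is chosen, take logs of both baseline and week-12 values and report a ratio of geometric means. Use the same form for calcium and phosphate with their own baselines.

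Report within-arm changes descriptively, and reword the 5.11 sentence so that relative efficacy is judged only by the between-arm comparison. Align the Part C summary with this.

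The cost is wording. The values are already on the case record form, and ANCOVA is a standard procedure in the software the protocol names. No extra patients, visits or assays are needed.

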### **5.13. The utilization of results:**

[figure not shown]
- The results will guide clinicians in selecting the optimal therapy for managing secondary hyperparathyroidism in hemodialysis patients, potentially favoring intravenous doxercalciferol over oral calcitriol, thereby improving patient outcomes and therapeutic strategies in nephrology practice.
- Efforts will also be made to present these results at conferences and publish them in peer-reviewed national and international journals.
- The results and observations of the study will be published as a thesis and submitted to the respective University as a part of the requirement for the MD (Nephrology) Phase-B examination purpose.
- The results of the study will be presented to the Department of Nephrology, CMCH.

**5.14. Ethical Implication:** The study will be conducted after the approval of the Ethical Review Committee of Chittagong Medical College. Voluntary written consent will be taken from the patient and legal guardians. All measures will be taken to protect anonymity. To do so, the name and address of the patient will be recorded on a separate sheet and specific codes will be put to the examination schedule and used for data collection. The interviews of the patient, clinical examination and investigations will be performed at the respective hospital after explaining the nature and purpose of the study to them, assuring that the information given by them will be used for the interest of the community and that the particulars of the patients will not be disclosed anyway.

**Time Schedule (GANTT CHART):**

	1st	2nd	3rd	4 th	5 th -6th	7 th -18 th	19 th -21 st	22 nd -23 rd	24th
Problem definition									
Literature review									
Research design									
IRB clearance									
Data collection									
Data analysis									
Report writing									
Submission									

**Part E**  
**Budget:**

Sl. No.	Head of expense	
		1st instalment
1	Research tools development	10,000/-
2	Office assistance for organizing the materials	5,000/-
3	Data collection (Investigation cost)	1,50,000/-
4	Drugs Cost	4,44,000/-
5	Data analysis	5000/-
6	Report composing	20,000/-
7	Printing	5,000/-
8	Stationaries	5,000/-
9	Transport/conveyance	1000/-
10	Miscellaneous	5000/-
	Total amount	6,40,000/-

**Appendix**  
**Case record form**

**Protocol Title: “Effects of Doxercalciferol Compared to Calcitriol For Lowering Parathyroid Hormone Level in Patients on Hemodialysis.”**

Patient’s identification			
1	Patient ID No.		
2	Contact no:		
3.	Group: Group 1: Experimental Group Group 2: Control Group		
Demographic characteristics			
1	Age:	.....years	
2	Sex:	0=Female 1=Male	
3	Group:	1=Group 1, 2=Group 2	
4	Monthly Income:	.....BDT	
5	Height:	.....cm	
6	Weight:	..... kg	
7	BMI:	..... kg/m 	
Clinical Variables			
1	Primary disease of CKD:	1=GN,2=DM,3=HTN,4=Other s	
2	Duration of CKD diagnosis:	.....years	
4	Blood Pressure:	..... mmHg	
5	Duration of Hemodialysis:	..... months/years	
Baseline Biochemical Variables			
1	Serum Calcium (S. Ca):	..... mg/dL	
2	Serum Phosphate (Po4):	..... mg/dL	
3	Parathyroid Hormone (PTH):	.....pg/mL	
Follow-up at 12 Weeks			
1	Serum Calcium (S. Ca):	..... mg/dL	
2	Serum Phosphate (Po4):	..... mg/dL	
3	Parathyroid Hormone (PTH):	.....pg/mL	

	Adverse Effect		6 weeks	12 weeks
1	Nausea	N0= 0 Yes= 1		
2	Vomiting	N0= 0 Yes= 1		
3	Edema	N0= 0 Yes= 1		
4	Headache	N0= 0 Yes= 1		
5	Fatigue	N0= 0 Yes= 1		
6	Matallic test	N0= 0 Yes= 1		
7	Loss of appetite	N0= 0 Yes= 1		
8	Constipation	N0= 0 Yes= 1		
9	Withdrawal	N0= 0 Yes= 1		
10	Expired	N0= 0 Yes= 1		
11	Others	N0= 0 Yes= 1		

#### Outcome

	Complete the study per the Protocol 0= No 1= yes
	If not reason for drop-out 1. Adverse experience 2. Failure to return for follow-up 3. Patients refuse treatment 4. Patient died 5. Non-co-operation 6. Insufficient therapeutic response

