**Withdrawal criteria:**

- Drug intolerance or patient refusal to continue medication due to adverse effects like nausea, anorexia, vomiting, etc.
- The patient wanted to withdraw himself from the study.
- If any participant became pregnant during the study period.

**5.10 Data collection instrument:** A structured pretested case record form.

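### The case record form codes poor response, which is the trial's own outcome, as a drop-out reason that the withdrawal criteria do not contain, so judged non-responders may be lost or excluded from the week-12 iPTH comparison

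*Protocol*

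**What the plan says.** The Withdrawal criteria (in section 5.9, after the operational definitions) have three entries. The first reads "Drug intolerance or patient refusal to continue medication due to adverse effects like nausea, anorexia, vomiting, etc". The second is a personal decision to leave the trial, and the third is pregnancy.

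Section 5.11, under the 6-week evaluation, applies that list: "patients will be removed if any of the withdrawals mentioned above are observed".

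The Outcome page of the case record form has a completion item, "Complete the study per the Protocol 0= No 1= yes", and a negative answer leads to a list of reasons. Six are offered: adverse experience, failure to return, refusal of treatment, death, lack of co-operation and, as code 6, "Insufficient therapeutic response". There is no code for pregnancy.

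The first specific objective is "To detect and compare the reduction of serum parathyroid hormone (PTH) levels following treatment". Section 5.11 assesses efficacy by comparing week-12 values with baseline. The 6-week evaluation lists no iPTH, and the form has iPTH fields only at baseline and week 12. The trial is open label. The Summary leaves the primary analysis as either intention to treat or per protocol, and section 5.12 names no analysis set. For patients who miss visits or withdraw, the end of section 5.11 promises best efforts to document outcomes and a request for a final visit where applicable.

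**The concern.** A drop-out list that is longer than the withdrawal criteria is not in itself a fault. Death and failure to return are also on the form and not among the criteria, and they do no harm there. Code 6 differs because it is the efficacy outcome under another name. No threshold says what counts as insufficient, and the person deciding knows the treatment and holds a stated hypothesis that doxercalciferol is better.

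A patient given this code can fall out of the comparison in two ways. If the patient leaves before week 12, the week-12 iPTH may never be obtained. If the code is given once the week-12 value is known, the value exists, but the patient is recorded as not having completed per protocol and would naturally be left out of a per-protocol set. In both cases the loss depends on the quantity being compared. Losing high values lowers the mean of the arm that loses them, so uneven use of the code can favour either drug.

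**Working it through.** **Comparison of the texts.**

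| Reason | Withdrawal criteria | Form, Outcome page |
|---|---|---|
| Adverse effects or intolerance | yes | yes |
| Patient's wish or refusal | yes | yes |
| Pregnancy | yes | no |
| Failure to return, death, non-co-operation | no | yes |
| Insufficient response | no | yes |

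Only the last row depends on the outcome. Nothing in the protocol says that such a patient stays in follow-up or in the primary comparison.

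**Inputs for scale.** From section 5.8: 43 per arm plus a 15% drop-out allowance, 43 × 0.15 = 6.45, taken as 6, giving 49 per arm; SDs of 42 (control) and 90 (doxercalciferol); planned difference 342 − 279 = 63 pg/mL; two-sided 5%. (The 42.8 behind the 43 does not follow from the printed inputs: (1.96 + 0.85)² × (42² + 90²) / 63² = 19.6. That is a separate matter; the 49 per arm is taken here as given.)

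**Shift in the mean.** If the top fraction p = 6/49 = 0.122 of a normal distribution is lost, the cut-off is z = 1.16 and the mean falls by φ(z)/(1 − p) = 0.203/0.878 = 0.231 SD. That is 0.231 × 90 = 20.8 pg/mL, or 0.231 × 42 = 9.7 pg/mL. Simulated values for samples of 49 are 20.2 and 9.5. Against the planned difference, 20/63 is roughly a third.

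**False-positive rate.** Assumptions: normal iPTH, no true difference, 49 per arm, the k highest values lost from one arm and k at random from the other, Welch t-test, 40,000 runs. Repeat runs differ by up to about half a percentage point. The correlation of 0.6 is an assumption; it stands for selection on an earlier or imperfect indication of the week-12 value.

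| Setting | k = 0 | k = 2 | k = 3 | k = 6 |
|---|---|---|---|---|
| SD 90 in both arms, perfect selection | 5.2% | 8.0% | 10.4% | 21.1% |
| SD 42 in affected arm, 90 in the other | 4.9% | 5.9% | 6.9% | 10.5% |
| SD 90 in both arms, correlation 0.6 | 4.7% | 6.0% | 7.1% | 10.1% |

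Mean shifts for k = 2, 3 and 6 are 7.8, 11.2 and 20.2 pg/mL in the first row, 3.7, 5.2 and 9.5 in the second, and 4.7, 6.7 and 12.2 in the third.

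The result also depends on which arm loses patients. With the protocol's own SDs and perfect selection from the doxercalciferol arm (SD 90, control 42), the rate is about 15% for k = 3 and 35% for k = 6.

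**Direction when the planned difference is true** (protocol SDs, values lost from one arm only). Loss from the doxercalciferol arm moves the estimate from 63 to about 74 (k = 3) or 83 (k = 6). Loss from the control arm moves it to about 58 or 54.

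**The case against.** The strongest reply is that the form only records why a patient left. That is right. A reader might infer that the Outcome page is a second rule permitting removal for poor response, but the text does not say so: only the Withdrawal criteria set rules, and section 5.11 applies only those. What stands is that the form provides for an exit that those rules do not contain.

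A reader might also infer that a patient coded 6 before week 12 has no week-12 value. Section 5.11 undertakes to try to document outcomes in all circumstances and to ask for a final visit where applicable, so the value may be missing but need not be. The undertaking does not require a week-12 iPTH or say that it will be analysed.

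Nor is the problem wholly independent of the choice of analysis set. Where the code rests on the week-12 result, the value is already on the form and is lost only if the primary analysis is per protocol. Intention to treat with week-12 iPTH collected would remove the problem. The protocol has not committed to that.

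It might be said that nobody could judge response before week 12, as no iPTH is scheduled. The operational definition of calcitriol, however, refers to titration on iPTH, while the Treatment paragraph of section 5.11 states a single daily dose. These passages need reconciling. As they stand, interim iPTH values may be seen, possibly in one arm only.

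Finally, the 21% figure should not be read as an expected size. It supposes that the whole drop-out allowance of one arm consists of its highest values, that loss in the other arm is random, and that absolute iPTH decides, whereas the objective concerns reduction. The milder settings roughly halve it.

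**Conclusion.** The concern holds in a limited form. The form and the withdrawal criteria disagree on a reason that is the trial's outcome. In an open-label trial with an undecided analysis set and no stated retention rule, outcome-dependent loss from the week-12 comparison is possible in either direction.

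For six patients the false-positive rate is about 21% with perfect selection and SD 90 in both arms, and about 10% with SD 42 in the affected arm or a correlation of 0.6. For two or three patients it is about 6 to 11% across those settings. The protocol's own SD pair gives more if the loss falls on the doxercalciferol arm. All these figures assume normality and one-sided use of the code; they show scale and do not predict how often it would be used. The missing pregnancy code is a clerical mismatch with no bearing on the bias.

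**What to change.** 1. Reconcile the Withdrawal criteria with the drop-out list so that both documents name the same reasons for leaving the study.
2. Split the form's item in two: reason for stopping study treatment, and reason for leaving the study. Keep poor response under the first only. Deleting the code outright would hide the reason, because such patients would be recorded as refusing or not co-operating. Whether poor response is a ground for stopping treatment is for the investigators to settle; the point here concerns follow-up and analysis.
3. State in sections 5.11 and 5.12 that the scheduled week-12 iPTH is taken from every randomised patient who still consents, whether or not treatment was stopped, and is analysed in the assigned arm. State also that poor response is not a reason for exclusion from the primary analysis.
4. Add a pregnancy code, for alignment only.

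The cost is one edit to the form and a few sentences in the protocol. No extra patients or visits are needed, as the week-12 sample is already planned for all.
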